**Table 6: Total Blood Volume**

Visit	Tests	Total Volume (mL)
Screening	Hematology, chemistry/CK-MB, virus serology, immunology sample (AAV9 Ab only), diagnostic confirmation sample	16.9
Day -1	Hematology, chemistry, capillary blood gas	3.3
Day 2	Hematology, chemistry, capillary blood gas	3.3
Day 7	Hematology, chemistry/CK-MB, immunology sample (ELISA/ELISpot)	7.6-9.6 b
Day 14	Hematology, chemistry, immunology sample (AAV9/SMN Ab only)	3.3
Day 21	Hematology, chemistry, immunology sample (AAV9/SMN Ab only)	3.3
Day 30	Hematology, chemistry/CK-MB, immunology sample (ELISA/ELISpot)	7.6-9.6 b
Day 60	Hematology, chemistry/CK-MB,	3.6
Month 3/4/5/7/8/10/11/ 13/14/16/17	Hematology, chemistry	25.3
Month 6/9/12/15	Hematology, chemistry/CK-MB	14.4
End of Study/ET	Hematology, chemistry/CK-MB	3.6
Maximum Total Volume for Studya		96.2

ET = early termination

a Patients will have different numbers of monthly visits, depending on their age at dosing. Maximum total volume based on a maximum of 16 monthly visits, provided T-cell responses are not elevated at Day 30 requiring additional surveillance samples and virus serology is not positive at screening requiring additional testing

b Immunology sample for IFN- $\gamma$  ELISpots requires 4-6 mL whole blood. Immunology sample for ELISA requires 1 mL whole blood. When drawn at the same visit, 4-6 mL is sufficient for both assays.

In a case where sufficient blood cannot be collected from a patient, blood will be used in the following priority order with the first having greatest priority and last having the least priority:

1. Safety labs
  - a. Chemistry
  - b. Hematology
  - c. CK-MB
2. Interferon gamma (IFN- $\gamma$ ) ELISpots to detect T-cell responses
3. Serum antibody to AAV9 and SMN
4. Genetic reconfirmation testing

If there is not sufficient blood volume to include the genetic reconfirmation testing sample at the screening visit, patient must return before Visit 2. All patients must have genetic reconfirmation testing completed.

#### **12.1.10.1. Hematology**

Hematology analysis will include a complete blood count with differential and platelet count with smear. Samples will be collected and shipped in accordance with the laboratory manual provided by the central laboratory. Blood samples for hematology analysis will be collected at all scheduled visits except Day 1 and Day 3 ([Appendix 1](#)).

Immediate/same-day hematology analyses required during in-patient dosing, as determined by the Investigator, will be performed as per investigational site standard procedures at the local laboratory. Investigators will receive hematology results from all study visits from the central laboratory.

#### **12.1.10.2. Blood Chemistry**

Samples will be collected and shipped in accordance with the laboratory manual provided by the central laboratory. Blood samples for chemistry analysis will be collected at all scheduled visits except Day 1 and Day 3 ([Appendix 1](#)).

Immediate/same-day chemistry analyses required during in-patient dosing, as determined by the Investigator, will be performed as per investigational site standard procedures at the local laboratory.

Chemistry analysis will include the following at all study visits:

- Serum GGT
- AST/ALT
- Serum total bilirubin
- Direct bilirubin
- Albumin
- Glucose
- Total creatine kinase

- Creatinine
- BUN
- Electrolytes
- Alkaline phosphatase

Creatine kinase (CK-MB) will be collected at Screening, Day 7, Day 30, Day 60, every 90 days, and at End of Study.

Investigators will receive chemistry results from all study visits from the central laboratory (except Day -1).

### **12.1.10.3. Urinalysis**

Urine samples will be collected in accordance with the laboratory manual provided by the central laboratory at all study visits except Day 1 and Day 3 ([Appendix 1](#)). Day -1 urinalysis will be performed as per investigational site standard procedures at the local laboratory. Urinalysis will include the following parameters:

- Color
- Clarity/turbidity
- pH
- Specific gravity
- Glucose
- Ketones
- Nitrites
- Leukocyte esterase
- Bilirubin
- Blood
- Protein
- Red Blood Cell
- White Blood Cell
- Squamous epithelial cells
- Casts
- Crystals
- Bacteria
- Yeast

#### **12.1.10.4. Virus Serology**

The administration of an AAV vector has the risk of causing immune-mediated hepatitis. For patients who have HIV or positive serology for hepatitis B or C or Zika virus, administration of AAV vector may represent an unreasonable risk; therefore negative serology testing must be confirmed at screening, prior to treatment. These samples will be collected at screening ([Appendix 1](#)) and shipped in accordance with the laboratory manual provided by the central laboratory.

#### **12.1.10.5. Capillary Blood Gas**

Capillary blood gas will be completed locally at Day –1 and Day 2 ([Appendix 1](#)). A puncture or small incision will be made with a lancet or similar device into the cutaneous layer of the patient's skin at a highly vascularized area (heel, finger, toe). To accelerate blood flow and reduce the difference between the arterial and venous gas pressures, the area will be warmed prior to the puncture. As the blood flows freely from the puncture site, the sample will be collected in a heparinized glass capillary tube.

#### **12.1.10.6. Immunology Testing (ELISA and IFN- $\gamma$ ELISpots)**

Blood samples for immunology testing will be collected and shipped to the central laboratory in accordance with the laboratory manual to test for serum antibodies to AAV9 and SMN (ELISA), and to perform IFN- $\gamma$  ELISpots to detect T-cell responses to AAV9 and SMN. Blood samples will be collected at screening (ELISA anti-AAV9 only), Day 7, Day 14 (ELISA anti-AAV9/SMN only), Day 21 (ELISA anti-AAV9/SMN only), and Day 30 ([Appendix 1](#)). Additional sampling may be performed at subsequent time points if ELISpot value(s) continue to be elevated, based on further discussion with the Principal Investigator and Medical Monitor.

#### **12.1.10.7. AAV9 Antibody Screen in Mother**

There is potential that the biological mother of the patient may have pre-existing antibodies to AAV9 that may be transferred to the patient through breast milk or, theoretically, via placental transfer in utero. Informed consent will be requested from the biological mother of the patient to screen the mother for circulating antibodies to AAV9. Once informed consent has been obtained, the mother will have her blood drawn from a peripheral vein at screening and shipped to the central laboratory for screening of anti-AAV9 antibodies. Mothers who test positive for antibodies to AAV9 will be asked to refrain from further feedings with breast milk.

If AAV9 antibodies are identified, the patient must desist in consuming breast milk from the biological mother.

Patients consuming banked breast milk from donor sources that cannot be test for anti-AAV9 antibodies must be transitioned to formula prior to participation.

#### **12.1.10.8. Blood for Diagnostic Confirmation Testing**

A blood sample will be collected during the screening visit and shipped to the central laboratory in accordance with the laboratory manual for reconfirmation of *SMN1* deletions/mutations, *SMN2* copy number, and absence of exon 7 gene modifier mutation (c.859G>C). This will be done to ensure consistency in diagnostic testing practices.

#### **12.1.10.9. Saliva, Urine, and Stool Collection**

Studies have shown that some vector can be excreted from the body for up to a few weeks after injection; this is called “viral shedding.” Vector shedding can be found in the blood, urine, saliva, and stool for up to 1 week following infusion. The potential health risks associated with the shed vector are not fully known at this time; however the health risk is thought to be low as the vector cannot replicate. Regardless, Institutional Review Board (IRB)/Independent Ethics Committee (IEC)-approved instructions should be provided to the patient’s family and care giver(s) regarding use of protective gloves if/when they come into direct contact with the patient’s bodily fluids and/or waste, as well as good hand-hygiene for a minimum of 2 weeks (14 days) after gene replacement therapy. Additionally, patients are prohibited from donating blood for 2 years following the vector infusion.

Saliva, urine, and stool samples will be collected for viral shedding studies at screening, 24 hours post-dose, 48 hours post-dose, Day 7, Day 14, Day 21, and Day 30 ([Appendix 1](#)). Samples will be collected, prepared, and shipped as per the laboratory manual.

A subset of patients at sites opting to participate in the viral shedding sub-study will have 24-hour total volume urine and fecal samples collected through 24 hour post-dose and through 48 hours-post dose.

## 13. ADVERSE AND SERIOUS ADVERSE EVENTS

### 13.1.1. Definition of Adverse Events

#### 13.1.1.1. Adverse Event

An AE is the development of an undesirable medical condition or the deterioration of a pre-existing medical condition following or during exposure to a pharmaceutical product, whether or not considered casually related to the product. In clinical studies, an AE can include an undesirable medical condition occurring at any time, including baseline or washout periods, even if no study treatment has been administered.

All adverse events that occur from the start of gene replacement therapy infusion through the last study visit will be collected and recorded in the eCRF.

All adverse events will be classified in accordance with the CTCAE version 4.03 outlined in [Table 7](#).

**Table 7: Common Terminology Criteria for Adverse Events**

Grade	Definition
1	Mild; asymptomatic or mild symptoms; clinical or diagnostic observations only; intervention not indicated
2	Moderate; minimal, local or noninvasive intervention indicated; limiting age-appropriate instrumental ADL. a
3	Severe or medically significant, but not immediately life-threatening; hospitalization or prolongation of hospitalization indicated; disabling; limiting self-care ADL. b
4	Life-threatening consequences; urgent intervention indicated.
5	Death related to AE.

Source: Common Terminology Criteria for Adverse Events (version 4.03) [9]

a Instrumental ADL refer to preparing meals, shopping for groceries or clothes, using the telephone, managing money, etc.

b Self-care ADL refer to bathing, dressing and undressing, feeding self, using the toilet, taking medications, and not bedridden.

Study enrollment will be interrupted should any patient experience an unanticipated CTCAE Grade 3, or higher adverse event toxicity that is possibly, probably, or definitely related to the gene replacement therapy. The event will then be reviewed by the DSMB and an evaluation will be made as to whether the study should be terminated early following the discontinuation rules.

Unanticipated CTCAE Grade 3 or higher adverse events that are possibly, probably, or definitely related to the gene replacement therapy must be reported within 24 hours to Sponsor and/or designee as per study safety management plan to ensure timely escalation to the DSMB.

### **13.1.1.2. Serious Adverse Event**

A SAE is an AE occurring during any study phase (e.g., baseline, treatment, washout, or follow-up), and at any dose of the investigational product, or comparator that fulfils one or more of the following:

- Results in death
- It is immediately life-threatening
- It requires in-patient hospitalization or prolongation of existing hospitalization
- Results in persistent or significant disability or incapacity
- Results in a congenital abnormality or birth defect
- It is an important medical event that may jeopardize the patient or may require medical intervention to prevent one of the outcomes listed above.

All SAEs that occur after signing of the informed consent through the last study visit, whether or not they are related to the study product, must be collected and recorded on forms provided by the Contract Research Organization.

### **13.1.1.3. Other Adverse Event**

The following specific treatment-emergent AE of special interest, which may be searched using Standardized Medical Dictionary for Regulatory Activities (MedDRA) queries, will be summarized:

- Elevated liver enzymes

Other adverse events (OAE) will be identified by the Drug Safety Physician and, if applicable, also by the Clinical Study Team Physician during the evaluation of safety data for the Clinical Study Report. Significant adverse events of particular clinical importance, other than SAEs and those AEs leading to discontinuation of the patient from the study, will be classified as OAEs. For each OAE, a narrative may be written and included in the Clinical Study Report.

## **13.2. Relationship to Study Product**

An Investigator who is qualified in medicine must make the determination of relationship to the investigational product for each AE (Unrelated, Possibly Related or Probably Related). The Investigator should decide whether, in his or her medical judgment, there is a reasonable possibility that the event may have been caused by the investigational product. If no valid reason exists for suggesting a relationship, then the AE should be classified as “unrelated.” If there is any valid reason, even if undetermined, for suspecting a possible cause-and-effect relationship between the investigational product and the occurrence of the AE, then the AE should be considered “related.”

If the relationship between the AE/SAE and the investigational product is determined to be “possible” or “probable” then the event will be considered related to the investigational product for the purposes of expedited regulatory reporting.

### **13.3. Recording Adverse Events**

Adverse events spontaneously reported by the patient and/or in response to an open question from the study personnel or revealed by observation will be recorded during the study at the investigational site. Information about AEs will be collected from the time of vector infusion until the end of the study. Serious Adverse Event information will be collected from signing of consent form until the last study visit. The AE term should be reported in standard medical terminology when possible. For each AE, the Investigator will evaluate and report the onset (date (and time if during Visit 2)), resolution (date (and time if start date during Visit 2)), intensity, causality, action taken, serious outcome (if applicable), and whether or not it caused the patient to discontinue the study.

It is important to distinguish between serious and severe AEs. Severity is a measure of intensity whereas seriousness is defined by the criteria under [Section 13.1.1.2](#). An AE of severe intensity may not be considered serious.

### **13.4. Reporting Adverse Events**

All SAEs (related and unrelated) will be recorded from signing of consent form until the last study visit. Any SAEs considered possibly or probably related to the investigational product and discovered by the Investigator at any time after the study should be reported. All SAEs must be reported to AveXis or designee within 24 hours of the first awareness of the event. The Investigator must complete, sign and date the SAE pages, verify the accuracy of the information recorded on the SAE pages with the corresponding source documents, and send a copy by fax or e-mail to AveXis or designee.

Additional follow-up information, if required or available, should all be faxed or e-mailed to AveXis or designee within 24 hours of receipt and this should be completed on a follow-up SAE form and placed with the original SAE information and kept with the appropriate section of the eCRF and/or study file.

AveXis is responsible for notifying the relevant regulatory authorities of certain events. It is the Principal Investigator's responsibility to notify the IRB or IEC of all SAEs that occur at his or her site. Investigators will also be notified of all unexpected, serious, product-related events (7/15 Day Safety Reports) that occur during the clinical study. Each site is responsible for notifying its IRB or IEC of these additional SAEs.

## 14. STATISTICS

This section summarizes key aspects of the analysis plan including definitions of co-primary, co-secondary, and [REDACTED] and safety endpoints, and the methods to be used to test the primary effectiveness hypothesis. Additional details regarding methods for the final data analysis will be provided in a separate Statistical Analysis Plan (SAP) which will be finalized and submitted to the Investigational New Drug application prior to the enrollment of the first patient. The SAP will detail all analyses and data displays, and will be executed according to Standard Operating Procedures in a controlled environment.

### 14.1. Study Endpoints and Populations

#### 14.1.1. Study Endpoints

The primary and efficacy endpoint will be compared to the null. The survival co-primary efficacy variable will be evaluated relative to literature-based historical controls (such as the Pediatric Neuromuscular Clinical Research Network [PNCr] [21]). These were selected on the basis of comparability to the target population and similarity to the investigational device.

##### 14.1.1.1. Co-Primary Efficacy Endpoint

The co-primary efficacy endpoints are:

- The proportion of patients that achieve functional independent sitting for at least 30 seconds at the 18 months of age study visit. It is defined by the Bayley Scales of Infant and Toddler Development (Version 3) ([Appendix 3](#)), confirmed by video recording, as a patient who sits up straight with the head erect for at least 30 seconds.
- The survival at 14 months of age. Survival is defined by the avoidance of the combined endpoint of either (a) death or (b) permanent ventilation, which is defined by tracheostomy or by the requirement of  $\geq 16$  hours of respiratory assistance per day (via non-invasive ventilatory support) for  $\geq 14$  consecutive days in the absence of an acute reversible illness, excluding perioperative ventilation. Permanent ventilation, so defined, is considered a surrogate for death.

An “acute reversible illness” is defined as any condition other than SMA that results in increased medical intervention (e.g., increased requirement for respiratory support; use of other concomitant medications as rescue) requirements and is expected to be reversible or improved following definitive intervention (e.g., surgery, antibiotics) or introduction of escalated supportive care, such as hospitalization (e.g., for upper respiratory infection, spontaneous fracture). The specific duration of the condition antecedent intervention shall not be considered in the definition of “acute.” The date of “definitive intervention” shall be defined as the date of provision of a procedure (e.g., surgery, etc.) or medication (e.g., antibiotics) intended to cure or substantially improve the condition. For conditions such as viral respiratory infections for which supportive care is provided, the date of “definitive intervention” shall be considered the date of hospitalization or substantial escalation of care.

█ [REDACTED]  
█ [REDACTED]  
█ [REDACTED]  
█ [REDACTED]  
█ [REDACTED]  
█ [REDACTED]

#### 14.1.1.4. Safety Endpoints

Assessment of the safety and tolerability of AVXS-101 treatment, including:

- Incidence of elevated LFTs and/or unresolved LFEs
- Incidence of CTCAE Grade 3 or higher toxicity, treatment-emergent adverse events
- Clinically significant changes in laboratory values, physical exams, cardiac assessments or vital signs
- Research Immunology Blood Labs including serum antibody to AAV9 and SMN as well as IFN- $\gamma$  ELISpot to detect T cell responses to AAV9 and SMN

#### 14.1.2. Statistical Analysis Populations

##### 14.1.2.1. Intent-to-Treat Population (ITT)

The ITT population will consist of symptomatic patients with bi-allelic deletion mutations of *SMN1* (exon 7/8 common homozygous deletions) and 2 copies of *SMN2* without the known gene modifier mutation (c.859G>C) who receive an IV infusion of AVXS-101 at less than 180 days of age. The first three patients enrolled must meet the criteria for the Intent-to-Treat Population.

##### 14.1.2.2. Efficacy Completers Population

The efficacy completers analysis population will consist of:

- All treated patients who reach 14 months of age, OR
- All treated patients who meet discontinuation criteria, discontinue the study due to an AE or death

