whether the AVXS-101 treated patients achieve a response rate greater than 0.1%. Based upon preliminary results from the ongoing Phase 1 clinical study AVXS-101-CL-101, at least 40% of treated patients in the ITT population are expected to achieve the co-primary efficacy endpoint of functional independent sitting for at least 30 seconds at the 18 months of age visit. With the assumption for the true response rate of AVXS-101 for the primary endpoint being in the range of 30% - 40%, a sample size of 15 patients that meet ITT criteria will be enrolled and assuming approximately 30% of patients are excluded from analysis, would yield an ITT population that would provide power of > 90% to detect a significant difference from 0.1% with  $\alpha = 0.025$  using a 1-sided exact test for a binomial proportion.

The second co-primary efficacy endpoint of survival at 14 months of age will be evaluated by comparing the results observed in the ITT population with the results from the age and gender-matched control patients selected from existing natural history data sets (PNCr) [*Neurol.* 2014; 83(9):810-817]. It is anticipated that 75% of patients in the PNCr population would not survive beyond 13.6 months of age, and that these control patients will represent a 25% survival rate based upon the natural history of the disease. Based upon preliminary results from the ongoing Phase 1 clinical study (AVXS-101-CL-101), at least 80% of patients in the ITT population are expected to survive, as defined, through 14 months of age. With this efficacy, an enrolled sample size of 15 patients that meet ITT criteria (assuming 30% of patients are excluded from the analysis) would yield an ITT population that would provide power of > 80% to detect a significant difference from the historical control with  $\alpha = 0.05$  using a 2-sided Fisher's Exact test.

9.2.1.	Prophylactic Administration of Prednisolone.....	37
9.2.2.	Prohibited Medications.....	38
9.3.	Treatment Compliance.....	38
9.4.	Randomization and Blinding.....	38
10.	STUDY PRODUCT MATERIALS AND MANAGEMENT.....	39
10.1.	Study Product.....	39
10.2.	Study Product Dose and Dose Justification.....	39
10.3.	Study Product Packaging and Labeling.....	39
10.4.	Study Product Storage.....	39
10.5.	Study Product Preparation.....	40
10.6.	Study Product Administration.....	40
10.7.	Dose Adjustment Criteria.....	40
10.8.	Study Product Accountability.....	40
10.9.	Study Product Handling and Disposal.....	40

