##### 14.1.2.3. All Enrolled Population

The all enrolled population will consist of all patients who receive an IV infusion of AVXS-101. Analyses of endpoints in this population are considered descriptive.

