### 14.2. Sample Size Calculation

This is a pivotal Phase 3, open-label, single-arm, single-dose, study assessing the efficacy and safety of AVXS-101 (gene replacement therapy) in up to twenty (20) patients with spinal muscular atrophy (SMA) Type 1 who meet enrollment criteria, may be either symptomatic or pre-symptomatic and are genetically defined by no functional survival motor neuron 1 gene (*SMN1*) with 1 or 2 copies of survival motor neuron 2 gene (*SMN2*) and who are < 6 months (< 180 days) of age **at the time** of gene replacement therapy (Day 1). Enrolling up to twenty (20) patients under the broader enrollment criteria is projected to enable enrollment of at least fifteen (15) patients that meet the Intent-to-Treat Population (ITT) criteria. The ITT population is identified as symptomatic patients with bi-allelic *SMN1* deletions and 2 copies of *SMN2* without the *SMN2* gene modifier mutation (c.859G>C) and will comprise the primary population for evaluation of the primary and secondary endpoints. Study power is based upon efficacy analysis of the ITT population. Furthermore, the first three patients enrolled must meet criteria for the Intent-To-Treat Population to enable a comparison of CHOP-INTEND scores at one-month following gene replacement therapy to enable a comparison of patient response between AVXS-101-CL-303 patients and Cohort 2 patient results from the Phase 1 trial (AVXS-101-CL-101). Patients with 1 copy of *SMN2*, pre-symptomatic patients and patients with the *SMN2* gene modifier mutation (c.859G>C) and other permutations outside of those specified in the ITT population will be evaluated separately as part of additional subgroup analyses. Details of all analyses will be contained within the Statistical Analysis Plan.

The two co-primary efficacy endpoints will be assessed in sequence: The endpoint of functional independent sitting will be assessed first and, only if this assessment meets statistical significance will the endpoint of survival be assessed.

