#### 14.3.2. Primary and Secondary Efficacy Analysis

Primary and secondary efficacy analyses will be based on the ITT population, those patients that are symptomatic with bi-allelic deletion mutations of *SMN1* and 2 copies of *SMN2* without the *SMN2* gene modifier mutation (c.859G>C). These analyses are to test the superiority of AVXS-101 to the results from natural observation study (PNCR) [21].

The first co-primary efficacy hypothesis to be tested is:

$$\begin{aligned} \mathbf{H}_0: p_{AVXS-101} &= 0.1\% \\ &\textit{versus the alternative} \\ \mathbf{H}_a: p_{AVXS-101} &> 0.1\%, \end{aligned}$$

where  $p$  is the proportion of functional independent sitting for at least 30 seconds at the 18 months of age study visit.

The second co-primary efficacy hypothesis to be tested is:

$$\begin{aligned} \mathbf{H}_0: p_{AVXS-101} &= p_{HISTORICAL-FINKEL} \\ &\textit{versus the alternative} \\ \mathbf{H}_a: p_{AVXS-101} &\neq p_{HISTORICAL-FINKEL}, \end{aligned}$$

where  $p$  is the proportion surviving at 14 months of age.

Primary efficacy endpoints will be examined on the ITT population. Testing for the first co-primary endpoint, functional independent sitting will first be performed using 1-sided exact binomial test. Only if the null hypothesis of equality in proportion of functional independent sitting is rejected at  $p < 0.025$ , will the co-primary endpoint survival improvement be tested using 2-sided Fisher's Exact test on the ITT population, comparing to matched patients from natural observational study (PNCR). This hierarchy approach strongly protects the Type I error rate.

The hypothesis for both co-secondary efficacy endpoints to be tested is:

$$\begin{aligned} \mathbf{H}_0: p_{AVXS-101} &= 0.1\% \\ &\textit{versus the alternative} \\ \mathbf{H}_a: p_{AVXS-101} &> 0.1\%, \end{aligned}$$

where  $p$  is the proportion of patients maintaining the ability to thrive/are independent of ventilatory support.

One-sided exact binomial tests will be executed for secondary efficacy analyses on the ITT population.

A sensitivity analysis will be conducted by repeating the primary efficacy analysis on the efficacy completers analysis population.

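### The Efficacy Completers set is drawn from all treated children and cut at 14 months, so it cannot serve as a sensitivity analysis of the ITT co-primary results

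*Protocol*

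**What the plan says.** Section 14.1.2.2 of the protocol has two limbs. The first is "All treated patients who reach 14 months of age, OR"; the second is "All treated patients who meet discontinuation criteria, discontinue the study due to an AE or death". Neither mentions symptoms, *SMN1* deletion, *SMN2* copy number or the c.859G>C modifier. The ITT definition immediately before it (14.1.2.1) names all of these.

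The use of the set is fixed in section 14.3. Section 14.3.1 analyses the co-primary and co-secondary endpoints in both ITT and completers, with ITT primary and observed data used where data are missing. Section 14.3.2 adds: "A sensitivity analysis will be conducted by repeating the primary efficacy analysis on the efficacy completers analysis population".

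Three other statements bear on this:
- All Enrolled (14.1.2.3) is every infused patient, and "Analyses of endpoints in this population are considered descriptive".
- Section 14.2 says that one-copy, pre-symptomatic and modifier patients, and other permutations "outside of those specified in the ITT population will be evaluated separately as part of additional subgroup analyses".
- The first co-primary endpoint (14.1.1.1) is "The proportion of patients that achieve functional independent sitting for at least 30 seconds at the 18 months of age study visit". Thriving and ventilator independence are also 18-month endpoints; survival is the only 14-month one.

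**The concern.** A sensitivity analysis should ask the primary question again under a different handling of whatever makes the primary result uncertain, here chiefly missing outcomes and discontinuation. This one instead changes the disease population.

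It brings in children whom the plan says it will keep apart, and tests them against a null not argued for all of them. The synopsis bases the near-zero sitting rate on two *SMN2* copies without the modifier, and section 14.2 bases it on the ITT population. Neither covers one-copy or modifier children.

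The 14-month cut is also wrong for three of the four endpoints. A child seen at 14 months but not at 18 is a completer with no sitting outcome, and the observed-data rule then removes that child from the calculation. At stake is how the result is read: agreement would look like robustness, and disagreement could reflect case mix alone.

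**Working it through.** **Inputs.** Up to 20 treated and at least 15 ITT (synopsis, 7.2); null 0.1%, one-sided exact binomial, alpha 0.025; assumed sitting rate 30-40%; about 30% excluded, so 15 becomes 10 or 11; 26 matched controls, 25% control survival, 80% treated survival, two-sided Fisher test at 0.05 (14.2, 14.3.2).

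**The plan's own power figures reproduce.** The critical value is one sitter, so power = 1 − (1 − p)^n.
- n = 10: 1 − 0.7^10 = 97.2%; 1 − 0.6^10 = 99.4%.
- n = 11: 98.0% and 99.6%.
- The stated figure is above 90%. Enumerating the Fisher test for 80% against 25% with 26 controls gives 81.9% (n = 10) and 85.9% (n = 11), against a stated figure above 80%.

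**How much of the set is outside ITT.** At most 20 − 15 = 5, and 5/20 = 25%. Every reason for withdrawal in section 8.3 is a discontinuation criterion, so the two limbs together take in nearly every infused child.

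**Sitting, when the ITT test succeeds.** One sitter gives p = 1 − 0.999^n:

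| n | p |
|---|---|
| 15 | 0.0149 |
| 16 | 0.0159 |
| 20 | 0.0198 |
| 25 | 0.0247 |
| 26 | 0.0257 |

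An ITT child who sits at 18 months has passed 14 months and is therefore a completer. With at most 20 treated, a significant ITT result always carries over. The completers test cannot disagree with it.

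**Sitting, when no ITT child sits.** One non-ITT sitter among 20 gives p = 0.0198, below 0.025. Under the plan's assumed rates, the chance of no ITT sitter is:
- n = 15: 0.7^15 = 0.5% and 0.6^15 = 0.05%.
- n = 10: 0.7^10 = 2.8% and 0.6^10 = 0.6%.

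If AVXS-101 left ITT children at the null rate, the chance of a significant completers test would be 1 − 0.999^15 × (1 − q)^5, where q is the non-ITT sitting rate. The documents give no q, so a range is shown: 24% at q = 5%, 42% at 10%, 77% at 25%, 97% at 50%. In ITT alone it is 1 − 0.999^15 = 1.5%.

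**Survival.** The number of surviving controls is an assumption: 25% of 26 is 6.5, so 6 and 7 are both shown. Two-sided Fisher p-values:

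| Treated survivors | 6/26 controls | 7/26 controls |
|---|---|---|
| 8/15, ITT only | 0.086 | 0.108 |
| 13/20, five non-ITT survivors added | 0.007 | 0.016 |
| 8/20, five non-ITT non-survivors added | 0.33 | 0.53 |

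The ITT data are the same in each column; only the case mix changes.

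**The case against.** The strongest reply is that nothing decisive depends on this set. ITT is the primary analysis, and survival is tested only after sitting is rejected in ITT. A reader might infer that a lone pre-symptomatic or modifier sitter could confirm or rescue the primary result. The documents do not support that. If no ITT child sits, the primary has failed and the completers p-value opens nothing; if one sits, the primary has already succeeded without help. That stands.

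Three further objections also stand:
- One sitter suffices because of the 0.1% null, not because of this definition. Restricting the set to 15 ITT children still gives p = 0.0149 for one sitter.
- The direction of bias is not fixed. One-copy children are eligible, and section 5.2 reports that all 9 one-copy patients in one series lived less than 11 months. They could pull the result down.
- Five is a ceiling. Enrolment stops as soon as practical after the fifteenth ITT patient, so few or no non-ITT children may be treated.

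It can also be said that the 14-month cut suits the survival endpoint and that the second limb rightly keeps deaths and discontinuations in the set. Both are true, but neither makes 14 months a completion point for sitting, thriving or ventilation.

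Leaving the matter to the SAP does not answer the point. The protocol itself states the definition and assigns its use, so a narrower SAP definition would contradict it.

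**Conclusion.** The point holds as a defect in the stated sensitivity analysis, not in the primary decision. As written, the set nearly duplicates the descriptive All Enrolled set, pools up to 25% of children whom section 14.2 says are evaluated separately, and uses a cut that is four months early for the 18-month endpoints.

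For sitting, the analysis is uninformative when ITT succeeds. When ITT fails it can be significant through one non-ITT child, but the chance of no ITT sitter is only 0.05% to 2.8% under the assumed 30-40% rate. For survival, the same 8/15 ITT result can read as p = 0.007 or p = 0.33 depending on five non-ITT children, assuming 6/26 surviving controls.

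These sizes assume the full 20 are treated with 15 in ITT. The definition checked is that of protocol version 2.0, and version 1.0 has the same one. The file also holds the end of a change log for what appears to be a later version whose body is not in the part supplied, so the current wording should be confirmed.

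**What to change.** Define Efficacy Completers as a subset of ITT. Tie membership to the 18-month assessment for sitting, thriving and ventilator independence, and to 14-month status for survival. Keep deaths and disease-related discontinuations in the denominator as failures; without that, the set would largely repeat the observed-data ITT analysis. Report non-ITT children only in the subgroup tables and the descriptive All Enrolled tables, as sections 14.2 and 14.1.2.3 already imply.

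The cost is one definition in the protocol, carried into the SAP, with no new patients or data. It does not change the one-responder threshold, which would have to be taken up through the 0.1% null.
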